6.3.3.2 Analysis of the GMFM-88

In addition, we will perform a secondary analysis of the GMFM-88 based on the cohort designation in AGS subjects based on their baseline AGS scale. As described earlier, the AGS scale is simple enough to be able to be applied retrospectively, based on clinical notes; this allowed us to develop a historical control cohort for comparison. Based on our pilot data, we have defined three cohorts for this study (Table 3) according to baseline neurologic function as measured by the AGS scale. The more severely affected individuals, due to floor effect, will use the AGS scale as a primary

outcome measure. Individuals with baseline AGS scales of \geq 9 have measurable function on the GMFM-88 and other functional assessments and this can be applied to this population.

Changes in GMFM-88 will first be compared between AGS cohorts descriptively, including graphical displays (e.g. overlaid lowess curves for each outcome versus treatment day, by cohort). GEE models will be fitted that model change in outcome over time; these models will include indicator variables for cohorts B and C (with cohort A as reference) and time by cohort interaction terms. Different parameterizations of time will be considered and the fit of models will be compared using goodness of fit criteria for GEE.

 Table 3. Cohort designation in AGS subjects based on baseline AGS scale.

AGS cohort				
Α.	AGS scale 0-3			
В.	AGS scale 4-8			
С.	AGS scale 9-11			

6.3.3.3 Analysis of the ISG scores

Initial analyses will be descriptive (see section 6.3.1). GEE and QLS models will also be fitted, using the same approaches that were described for AGS scale (see sections 6.3.2 and 6.3.3.1). In addition, quantile regression may be applied to evaluate change in median ISG.

6.3.3.4 Analysis of symptoms diaries scores

Initial analyses will be descriptive (see section 6.3.1). GEE and QLS models will be fitted for evaluation of symptoms diaries scores, using the same approaches that were described for AGS scale (see sections 6.3.2 and 6.3.3.1) but potentially with some adjustment for differential timing of measurement.

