4.3 Screening Visit

Screening (Visit 1) is applicable only to subjects not transferred from the JAGA Compassionate Use study (CHOP IRB Study #13205). The screening visit is a 2- to 28day period beginning at Visit 1. After receiving written informed consent from the patient's parent or a legal guardian (hereafter, "parent" refers to "parent or legal guardian"), patients will be assigned a patient number and will be considered entered into the study and study procedures may begin. Entry procedures will be performed per the Study Schedule (Appendices 1 and 2). During the screening period, patients must complete at least 14 days of diary entries before receiving the first dose of baricitinib (refer to the Patient Diary and Diary Score section below and Appendices 5 and 6). Current use of concomitant medications and reasons for use will also be collected on the eCRF, as well as start and stop dates. Particular note will be made of medications that are contraindicated (see Section 3.4.2) and which require dose adjustment (see Section 4.4).

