6.2 Secondary Endpoints

Secondary endpoints will include the following:

- Improvement of the AGS scale from Screening to Treatment over time.
- Improvement of the GMFM-88 between Screening and Treatment over time.
- The change in Interferon Signaling gene score between Screening and Treatment over time.
- The change in skin symptoms between Screening and Treatment over time using the CLASI.
- Safety and tolerability of DRUG based on Adverse Events (including laboratory abnormalities).
- Change in AGS disease severity score (daily diary) between Screening and two years of treatment.

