6.3.2 Primary Outcome Analysis

As is often the case in a study of a rare disease, we face a number of challenges in our analysis. The number of available patients with AGS is limited, so that our sample size is small. This protocol grew out of a compassionate use trial, so that randomization could not be employed to assign patients to receive treatment (or not). The temporal spacing of measurements differs between treated patients versus historical controls. As a result of these features, there are limitations to many of the standard statistical approaches. Our approach will therefore be to apply a recommended approach for efficacy, but to also apply several sensitivity analyses. Our goal will be to demonstrate efficacy for several statistical approaches, as we achieved in our analysis of preliminary data.

Our efficacy analysis for our primary outcome will apply the method described in Section 15.4 of Fitzmaurice, Laird, & Ware⁷⁴ that decomposes longitudinal effects of treatment versus cross-sectional effects due to participants starting treatment at different ages. We will first create a time for each patient that is negative prior to treatment and is positive after treatment. We will then fit a GEE model that includes time within patients, an indicator variable for treatment and a time by treatment interaction term. If the interaction term is significant, this will indicate that the change over time in AGS score (slope) is different after treatment, versus before. If the interaction term is not significant, it will be removed and the model will be fitted with time and the indicator variable for (post) treatment. If the indicator variable differs significantly from zero, this will indicate that the AGS score is higher on average, post-treatment. To compare values at baseline and 52 weeks post baseline, different parameterizations of time (continuous versus indicator variables at different visits) will be considered and analyses will also be performed on data restricted to values measured at baseline and 52 weeks post baseline. This approach will first be applied to patients who are eventually treated. to compare their AGS scores pre versus post-treatment.

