- s. Functional outcome assessments will be conducted at baseline and every six months.
- t. Three baseline IFN scores will be collected, each at least 5 days apart and not more than 60 days before start of study medication.
- u. Patients will be monitored for BK viremia at baseline, and every six months until they reach two years of age. Over two years of age, complete follow-up BK testing will be performed if any of the following is observed: blood in urine (as defined by 5-10 RBCS in HPF), protein in urine (positive), decrease in eGFR (30 <60 mL/min/1.73 m²). Follow- BK testing includes urine and serum BK testing. Abnormal urine results with urinary tract infection, in the absence of change in eGFR, do not necessitate BK testing.
- v. The creatinine should be measured using the IDMS (Isotopic Dilution Mass Spectrometry) technique to monitor the eGFR if available. Other methods are allowed but are not preferred. Laboratory testing using other methods will not be used to monitor the eGFR.
- w. These labs may be drawn (optional).
- x. For bone growth monitoring, IGF-1 will be completed yearly, and hand/wrist/fingers X-rays will be completed at baseline, 6 months, 12 months and then every 12 months (not after a bone age demonstrating complete growth).

* Visit schedule will be extended beyond Week 288 to long term follow up if transition to commercial supply is not possible for a patient. Visit will then be extended until patient transitions to commercial supply. The same tests and procedures that were completed during the study will be continued. Visit numbers will continue per the same numbering logic (232, 233, 234...).

Appendix 3. Dose Escalation Schedule for Patients with eGFR ≥60 mL/min/1.73 m2 or Normal eGFR for Age <24 Months (see footnote below^c)

If a change in the patient's weight during the study would place the patient in a different weight range, changes over time are permitted.

		Morning Dose	Noon Dose	Afternoon Dose	Evening Dose	Total Daily Dose	Dosing Frequency
FR ≥ 60 mL/min/1.73	m ²						
5-< 10 kg	Initial	1 mg	1 mg	0 mg	1 mg	3 mg	TID
	Escalation 1	1 mg	1 mg	1 mg	1 mg	4 mg	QID
10-< 20 kg	Initial	2 mg	2 mg	0 mg	2 mg	6 mg	TID
	Escalation 1	2 mg	2 mg	2 mg	2 mg	8 mg	QID
20-< 40 kg	Initial	3 mg	-	0 mg	3 mg	6 mg	BID
	Escalation 1	3 mg	—	2 mg	3 mg	8 mg	TID
≥ 40 kg	Initial	4 mg	_	-	4 mg	8 mg	BID
	Escalation 1	5 mg	—	_	5 mg	10 mg	BID
	Escalation 2	6 mg	_	_	6 mg	12 mg	BID

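### The diary endpoint is the change from Screening to two years, but section 6.3.3.4 leads with a slope-then-level model that, with about two weeks of pre-dose diary, understates gradual improvement

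*Combined protocol and SAP*

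**What the plan says.** Section 6.2 lists the endpoint as "Change in AGS disease severity score (daily diary) between Screening and two years of treatment". For its analysis, 6.3.3.4 starts with the descriptive summaries of 6.3.1 and then states "GEE and QLS models will be fitted for evaluation of symptoms diaries scores, using the same approaches that were described for AGS scale", citing 6.3.2 and 6.3.3.1, "but potentially with some adjustment for differential timing of measurement". That adjustment is not defined.

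The lead approach in 6.3.2 has two steps. First: "We will then fit a GEE model that includes time within patients, an indicator variable for treatment and a time by treatment interaction term". When this test fails to reach significance, "it will be removed and the model will be fitted with time and the indicator variable for (post) treatment", and that indicator is read as the treatment effect.

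On the amount of diary data, section 4.3 requires that "patients must complete at least 14 days of diary entries before receiving the first dose of baricitinib". Footnote i of Appendix 2 repeats the two-week minimum, and section 1.5 gives the same minimum for the compassionate-use programme. Section 5.2.3 asks for two years or more of diaries on treatment. Section 4.2 allows a pre-screening period of 2 weeks to 6 months with diaries. It applies only where information on prior care is insufficient, and not to patients transferred from the compassionate-use study.

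**The concern.** The slope-then-level rule was written for the AGS scale, which can be scored back in time from clinical notes. The diary has no such history. At the required minimum, the pre-treatment part is 14/(14 + 730) = 1.9% of the time axis. A slope fitted to it is almost pure noise, so the interaction will rarely be significant. Once it is removed, the single time slope is in effect the on-treatment slope, and the indicator measures only a jump at the first dose.

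The result would then depend on how fast benefit arrives rather than on the change that 6.2 names. QLS does not alter this, because it changes how the correlation is estimated and leaves the mean model as it is. At stake is a named secondary endpoint for which the cross-referenced analyses can give opposite answers, with no statement of which one leads.

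**Working it through.** **1. The plan's own figure.** Section 6.4 gives 98.3% power for 30 pairs at effect size 0.77 (two-sided paired t-test, alpha 0.05), and 80% at 0.53. The noncentral t with 29 degrees of freedom gives 98.27% and 80.1%, so both reproduce. They concern the AGS scale; no power is stated for the diary.

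**2. Precision of the pre-treatment slope.** With T daily entries, n patients and independent errors of daily SD 1, the SE of the mean pre-treatment slope, scaled to two years, is 730 / √(n × T(T² − 1)/12). For T = 14, T(T² − 1)/12 = 227.5.
- n = 45: 730/√(45 × 227.5) = 7.2 daily SDs
- n = 30: 730/√(30 × 227.5) = 8.8 daily SDs

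For 80% power the two-year slope difference would have to be about 2.8 × 7.2 ≈ 20 daily SDs, which is implausible.

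**3. What the indicator estimates once the interaction is dropped.** The model (intercept, time, post indicator) was fitted without noise to 14 flat pre-dose days and 730 on-treatment days. No diary SD is needed. The range covers AR(1) 0.5 weighting (lower figure) and independence weighting (higher figure).

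| Assumed course | Share of the two-year change in the indicator |
|---|---|
| Levels off, time constant 30 days | 73–84% |
| 90 days | 52–59% |
| 180 days | 32–36% |
| 365 days | 15–18% |
| Linear over two years | about 0% |

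In the linear case the time term takes the whole change. A longer baseline does not repair this model: with 180 pre-dose days the 180-day share is 27–28%.

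**4. Detection.** Simulation used 2,000 trials per setting and the two-step rule at two-sided 0.05. The documents give no diary SD or effect, so these are assumptions: daily SD 1; AR(1) errors 0.5; flat before treatment; two-year improvement D of 1 daily SD; patient-level mean/SD of change 0.77, borrowed from the AGS figure. The direct contrast is the 14-day Screening mean against the last 14 days of year two.

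| Linear course, 14 pre-dose days | n = 45 | n = 30 |
|---|---|---|
| Two-step rule | 5.0% | 5.0% |
| Direct contrast | 99.6% | 95.1% |
| Paired pre/post averages (Table 2 of 6.3.3.1) | 98.9% | 91.7% |

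With D from 0.5 to 2 the two-step figure is 4.9–5.6%. With autocorrelation from 0 to 0.8 and several working correlations (n = 45, D = 1) it is 4.0–5.4%.

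**5. Dependence on shape and on baseline length (D = 1).** For improvement that levels off, with 14 pre-dose days, two-step detection is:

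| Time constant | n = 45 | n = 30 |
|---|---|---|
| 7 days | 97.1% | 95.1% |
| 30 days | 97.6% | 93.9% |
| 90 days | 97.3% | 91.6% |
| 180 days | 94.4% | 82.7% |
| 365 days | 51.9% | 40.1% |

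For a linear course at n = 45, if every patient had a longer baseline diary, detection would be 5.0% (28 days), 23% (90 days) and 83% (180 days).

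**The case against.** A reader might infer that the plan as a whole would miss a gradual diary benefit. The documents do not support that. The same cross-references bring in change from baseline with 95% CI and final minus baseline (6.3.1), visit indicators for time and a baseline-to-52-week restriction (6.3.2), and paired pre/post averages and a screening-versus-final test (Table 2 of 6.3.3.1). These would show a gradual gain. But Table 2 is worded for the AGS scale, and none of these analyses is fixed at two years for the diary. The pre/post average also estimates another quantity: half the two-year change if improvement is linear.

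A linear two-year course appears nowhere in the documents, and the responses with stated timing are fast: ISG scores and skin lesions at 72 hours (section 1.5). This stands as a limit on the power result. It does not remove the understatement, which is already 16–27% at a 30-day time constant (100% minus 73–84%).

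Fourteen days is a minimum, and pre-screening diaries may be longer for some patients. This also stands.

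A direct contrast credits any natural decline in symptoms to the drug, and section 1.1 describes an apparent burning-out of the disease in early life. That is a true limitation, but a two-week slope cannot estimate a pre-treatment trend, so it does not favour the existing model.

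Section 6.4 calls the secondary analyses mainly hypothesis-generating. That lowers the stakes, but it does not tell the analyst which diary result is the endpoint.

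It is also tempting to extend the point to the ISG score, since 6.3.3.3 reuses the same models. No loss has been shown there, the described response is rapid and quantile regression is also offered, so the point is not made for ISG.

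**Conclusion.** The point holds for the lead diary model. Section 6.3.3.4 does not pre-specify the contrast that 6.2 defines, and the model it reuses estimates something else when the pre-dose diary is close to the required minimum. The indicator recovers from about 84% of the two-year change (30-day time constant) down to about 36% (180 days) and about 0% (linear), under independence weighting. Near-linear improvement is detected in about 5% of simulated trials, against about 99% for the direct contrast with 45 patients. Benefit arriving mostly within about six months is usually detected (83–98% across 30 and 45 patients) but understated.

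The shares rest on the assumed response shapes. The detection rates also rest on assumed diary SDs and on an effect size borrowed from the AGS scale. The near-5% result held across the ranges tried with 14 pre-dose days. The plan should be changed here, although the matter concerns a secondary endpoint and other planned analyses partly cover it.

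**What to change.** In 6.3.3.4, name the endpoint's own contrast as the lead diary analysis. Either of two forms would serve:
- the within-patient mean diary score in a defined window at two years (for example the last 28 days) minus the Screening diary mean, with 95% CI and paired test; or
- preferably, a GEE with Screening as reference and indicators for on-treatment windows, which keeps patients who have no two-year diary.

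Fit no pre-treatment slope and use no stepwise removal in this analysis. Keep the slope-then-level model as descriptive. State that historical controls do not apply to the diary: the only source described for that cohort is AGS scoring from clinical notes (sections 1.5 and 6.3.3.2), yet the reference to 6.3.3.1 formally brings them in.

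The cost is SAP wording; the data are already collected and the analysis is simpler. The downside to state is that, without a control, the contrast cannot separate drug effect from natural decline in symptoms.

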6.3.3.5 Correlation of within participant changes in primary and secondary outcomes

In addition to individual analysis of each primary and secondary outcome, we will also evaluate the correlation of intra-subject changes in outcomes with Pearson or Spearman correlations, as appropriate. We hypothesize that as the inflammation is lowered (as shown by the IFN score decreasing), the clinical measures of inflammation will improve, as measured by the primary (AGS development score) and secondary outcomes (clinical diaries, GMFM-88).

6.3.3.6 Special considerations

As described earlier, subjects enrolled in the Compassionate Use Treatment Protocol I4V-MC-JAGA (JAGA Compassionate Use study, CHOP IRB Study #13205) for whom commercial supply is not available, will be reconsented to the investigator-initiated JAK inhibitor treatment in AGS study. Data collected as part of their participation in IRB #13205 will be included as part of their longitudinal analysis, including baseline studies. Additionally, subjects who did not transition to this investigator-initiated study because they obtained commercial supply or discontinued participation in I4V-MC-JAGA will be consented via a separate consent form to permit inclusion of their data. For subjects who are considered lost to follow-up (unable to be reached after multiple attempts), a waiver of consent and HIPAA authorization will apply for inclusion of their data. This comprehensive approach is important to overall understanding of efficacy and safety in this ultra rare disease.

Because the JAGA Compassionate Use study protocol and this protocol are carefully aligned, we do not anticipate that any observed within patient changes in study outcomes will be due to differences in procedures between the two studies. However, we will perform sensitivity analyses, to determine if changes in outcomes with treatment differ between the two groups (data from patients enrolled only in the JAGA Compassionate Use study, data from patients who have been enrolled in both the JAGA study and the investigator-initiated JAK inhibitor in AGS study versus data from patients who are solely enrolled in the JAK inhibitor in AGS study). To the GEE model that includes time within patients, an indicator variable for JAK inhibitor in AGS study and a three way interaction term that is constructed as the product of time and treatment and the study indicator. If the three way interaction term is significant, this will indicate that the impact of treatment (change over time with treatment) differs significantly between groups.

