4.4 Study Treatment Phase

4.4.1 Enrollment

Consent

Written informed consent from the patient/patient's parent or a legal guardian will be obtained in person by the study investigators prior to any study procedure, with the exception of blood and urine tests, and daily diaries, which may be completed from the pre-screening period, after verbal consent.

For the patients transferred from the JAGA Compassionate Use study (CHOP IRB Study #13205), written informed consent from the patient/patient's parent or a legal guardian will be obtained by the study investigators prior to any study procedure completed as part of this investigator-initiated study.

Additionally, all the JAGA subjects (including the patients who do not consent and transition to the investigator-initiated JAK inhibitor treatment in AGS study will be asked to sign a consent form to allow for their data collected as part of the compassionate use program to be used for data analysis as part of the investigator-initiated study. The JAGA subjects who do not transition to the investigator-initated study will sign a separate consent form while the subjects who transition will be re-consented with a revised informed consent form including mention of this data transfer. Statistical considerations of this data transfer are detailed in Section 6.

Inclusion criteria

Entered patients are eligible for enrollment into the study (that is, eligible to receive baricitinib) only if they meet inclusion criteria (Section 3.4.1) at the time of Visit 2 and don't meet the exclusion criteria listed in Section 3.4.2.

Exclusion from Study Enrollment

Entered patients are ineligible for enrollment (that is, ineligible to receive baricitinib) and should be discontinued from the study if they meet any of the exclusion criteria listed in Section 3.4.2.

Patients who are entered, but do not meet enrollment criteria, should be discontinued from the study. These patients can be re-entered into the trial (that is, be reconsented) if the investigator believes that the patient might meet enrollment criteria at a future date, taking into consideration the volume of blood required for rescreening. Patients will receive treatment as clinically indicated for infections regardless of treatment decisions for baricitinib.

Rationale for Exclusion of Certain Study Candidates

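### The check of new against compassionate-use patients lists no two-way study terms, and no 52-week estimate is planned for patients outside the preliminary data

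*Combined protocol and SAP*

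**What the plan says.** **Use of JAGA data.** Section 4.4.1 asks all JAGA patients, including those who do not transfer, to consent to "data collected as part of the compassionate use program to be used for data analysis" in this study. Section 6.3.3.6 says of those who transfer: "Data collected as part of their participation in IRB #13205 will be included as part of their longitudinal analysis, including baseline studies". It adds the data of consenting patients who did not transfer and, under a waiver, of those lost to follow-up.

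**Primary model.** Section 6.3.2 explains: "This protocol grew out of a compassionate use trial". Its GEE model has time, treatment and time x treatment, and "This approach will first be applied to patients who are eventually treated".

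**Check between studies.** Section 6.3.3.6 plans a sensitivity analysis to "determine if changes in outcomes with treatment differ between the two groups", setting JAGA patients against "data from patients who are solely enrolled in the JAK inhibitor in AGS study". The model sentence has no main verb. It names a study indicator and "a three way interaction term that is constructed as the product of time and treatment and the study indicator". The reading rule follows: "If the three way interaction term is significant, this will indicate that the impact of treatment" differs between the groups.

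**Estimates and power.** Section 6.3.1 plans changes from baseline with 95% CI, with 52 weeks as its example. Section 6.4 takes a mean change of 0.80 (CI 0.45 to 1.16) and SD 1.04 from 35 preliminary patients. It gives 98.3% power for 30 pairs in a paired t-test of pre- and post-treatment averages, and its drop-out paragraph then calls 30 patients adequate for the primary outcome.

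**The concern.** The check is the plan's only safeguard on combining the two sources. A three-way product without its two-way study terms is not a test of the three-way effect alone: it also absorbs any difference between the groups in background course. New and JAGA patients could differ in course because of age, disease stage or genotype, without any difference in response to the drug. The stated rule would still call that a treatment difference.

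The second issue is independence. If the patients who produced the 0.77 supply much of the efficacy analysis, the pooled p-value partly restates a known result. The direct way to see what the other patients add is an estimate in those patients. A p-value for the difference between groups does not supply it, and a non-significant one is weak reassurance when one group is small.

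**Working it through.** **1. The plan's own power figure.** Inputs from Section 6.4: n = 30, effect size 0.80/1.04 = 0.77, two-sided alpha 0.05. Noncentral t with 29 df and noncentrality 0.77 x sqrt(30) = 4.22 gives 98.3%, as stated. The effect size giving 80% power is 0.529, and 0.529 x 1.04 = 0.55 points, as stated. The arithmetic is right for that test.

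**2. How many patients lie behind the 0.77.** The stated CI has half-width (1.16 - 0.45)/2 = 0.355. The formula is t(0.975, n-1) x 1.04/sqrt(n):
- n = 30: 0.388
- n = 35: 0.357

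So it rests on about 35 treated pre/post pairs. Section 1.5 (Measurement of AGS Scale) reports 34 treated compassionate-use patients with scale data. With the statement on the protocol's origin in Section 6.3.2, this makes large overlap likely. No section states it.

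**3. Which test the 98.3% belongs to.** The test is the pre/post-average comparison, a sensitivity analysis in Table 2. The primary endpoint (Section 6.1) is the change from baseline to 52 weeks, whose SD is not given. If the mean 52-week change were also 0.80 (assumed), 30 patients would give:
- SD 1.04: 98%
- SD 1.3: 90%
- SD 1.5: 81%

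**4. The three-way term as listed.** Let background slope differ between groups by d points/yr, with the same treatment effect in both. New patients then deviate by d x time at every visit. In the listed model the only columns specific to them are a constant and post-treatment time, so post-treatment time takes up the deviation.

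Simulation settings, all assumed: 35 JAGA v 10 new patients; intercept SD 2; residual SD 0.5 or 1.0; random-slope SD 0 or 0.3/yr; exchangeable weights; robust SE; 4,000 runs per cell; two pre-treatment visits with one year of follow-up, four with two years. Percentage of runs in which the three-way term was falsely significant:

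| d (points/yr) | Listed, 1 year | Listed, 2 years |
|---|---|---|
| 0.05 | 8-10% | 9-23% |
| 0.1 | 9-13% | 14-57% |
| 0.3 | 19-54% | 58-100% |

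At d = 0.3 the mean coefficient was 0.38 (one year) and 0.45 (two years), where the true value is 0. With time x study and treatment x study added, the mean coefficient was about 0 and the false-positive rate 5-9% in every cell. With d = 0 the listed model gave 6-9%, so that excess over 5% is small-sample inflation of the robust SE. A separately programmed run at d = 0.3 gave about 32% (one year) and 96% (two years), against 7-8% with the two-way terms.

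**5. A difference in level only.** In another simulation (300 runs, assumed settings), new patients differed only by -0.8 points in post-treatment level. The listed three-way term was significant in 87% of runs, against 5% in the full model, where treatment x study carries the difference. A level difference is a treatment difference under Section 6.3.2, so the full model must be read on both terms.

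**The case against.** **The sentence is damaged, not a specification.** It has no main verb, so words may be missing, and an analyst might add the two-way terms by default. That is fair, and the simulated rates apply only to the model as listed. The text as it stands names none of these terms, while the reading rule is complete.

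**The settings are assumed and the check is secondary.** Both are true. At 0.05 points/yr and one year the excess is negligible (8-10% against 6-9%). Section 6.4 describes secondary analyses as mainly hypothesis-generating, so the check does not decide the primary result.

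**A 52-week estimate is already planned.** A reader might infer that none is. Section 6.3.1 does plan one with 95% CI. What is missing is the estimate for patients outside the preliminary data.

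**The number of new patients is unknown.** A reader might subtract 35 from the 45 evaluable or the 55 enrolled. The documents do not support this. The 55 in Section 3.2.2 counts JAGA patients who transfer. Section 3.1.1 limits transfer to those without commercial supply, and data from non-transferring patients are used as well. The number transferred is not given.

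**Two groups or three?** A reader might see a contradiction because three sets of patients are listed. The single contrast in the sentence most naturally puts both JAGA sets on one side, which fits one study indicator. The coding only needs to be written down.

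**The ingredients of the overlap are disclosed.** They are, in separate sections. The count and its consequence for the p-value are not stated.

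**Conclusion.** The concern holds on two linked points.

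First, the check as listed can report a different disease course as a different treatment impact. The size depends on the slope difference: from barely above nominal at 0.05 points/yr over one year to 58-100% at 0.3 over two years, under assumed visits and variances. The direction follows from the model's structure and does not depend on those settings.

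Second, the pooled efficacy result is not independent of the preliminary data to the extent that patients overlap, and the plan neither says so nor gives the estimate for the other patients. This rests on two inferences. One is that the 35 are largely JAGA patients. The other is that JAGA data enter the 52-week analysis: Section 6.3.3.6 stands under secondary analyses, but Section 4.4.1 is general and Section 6.3.2 covers everyone eventually treated.

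It would go too far to say that the 98.3% is wrong, since it reproduces exactly for its own test. What is unsupported is carrying the 30 patients over to the 52-week change. Nor do the documents show that pooling is improper: with so rare a disease it is defensible if disclosed.

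**What to change.** 1. **Section 6.3.3.6.** Replace the model sentence with: *The GEE model will include time, treatment, time x treatment, study, time x study, treatment x study and time x treatment x study.* Code study as 1 for patients enrolled only in this trial and 0 for all JAGA patients. Judge a difference in treatment impact on treatment x study together with the three-way term.
2. **Section 6.3.2.** Report the 52-week change with 95% CI for patients not in the preliminary data set, beside the pooled estimate. State that the pooled p-value is not independent of the preliminary data to the extent that patients overlap.
3. **Section 6.4 and the synopsis.** State how many evaluable patients contributed to the preliminary data. Say that the 98.3% and 80% refer to 30 independent pairs and the pre/post-average t-test, not to the 52-week change, and give the SD of that change or say that it is unknown.

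The cost is wording and one extra analysis; no data are discarded. The power statement becomes less favourable, and the restricted CI will be wide. By the formula in step 2, at SD 1.04 its half-width would be about 0.74 points with 10 patients, 0.49 with 20 and 0.39 with 30. These sizes are illustrative, because the actual number is not in the documents.
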